In summary: we have developed a promising multi-technology poly-anatomic approach to development of noninvasive sensing in the setting of occult hemorrhage. The year one and year two studies used a rack system composed of commercial impedance and optical components. After evaluating the performance of individual components, we have been able to “prune” the court technologies to: impedance tomography, impedance spectroscopy, NIRS, plethysmography and ECG. The impedance and optical technologies have been incorporated into a first-generation prototype.

Phase III Trauma Validation and Re-Training Trial

Approach/Methods

Summary: We will enroll 480 trauma patients in a “no significant risk” prospective clinical trial to: 1) evaluate the performance of our Mark I prototype, 2) validate the performance of the Phase II algorithm and 3) re-train the algorithm to Phase III iteration.

This is not a therapeutic study. All technologies are non-invasive.

The main outcome variables are non-invasive measurements that will be used for machine learning, not real-time patient management. The data generated will be used later for discovery and validation in traditional and innovative machine learning.

Inclusion criteria:

1. Age ≥ 18
2. Patients suffering blunt and/or penetrating trauma
3. Awake and alert with GCS ≥ 14 as indicated by the treating provider/care team
4. Triage systolic blood pressure greater than 90 and heart rate less than 120

Exclusion criteria:

1. Need for ongoing fluid or pressor support (standard local fluid resuscitation only)
2. Signs of clinically significant ongoing external hemorrhage with active bleeding documented on radiology/ultrasound during initial evaluation (approximately 15 minutes post ED arrival)
3. Respiratory distress with O₂ saturation <96%
4. Pre-existing systemic illness, likely to alter systemic cardiovascular response to hemorrhage (overt clinical heart failure). Including congestive heart failure, and a paced cardiac rhythm.
5. Pregnant
6. Prisoner status
7. Anatomical abnormality or injury that would prevent placement of the electro-optical electrodes

Screening and Enrollment: The study team will approach ED patients initially evaluated by the Trauma team/ED care team in the Trauma room and currently being observed in a general ED bed who had met inclusion criteria. Those patients will participate in the informed consent process with study personnel following departmental and hospital SOP.

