As a minimal risk study, there will be no change in the routine care of these patients.

Definition of hemodynamic deterioration - any of:

- A significant period (greater than 5 min.) of systolic blood pressure less than 90 associated with a heart rate greater than 110.
- 20% increase in HR from baseline
- 15% decrease in MAP from baseline
- Clinician defined need for greater than established initial fluid resuscitation (blood products intended to maintain blood pressure)
- A blood lactate result greater than 4 without nontraumatic causes of lactic acidosis

Study Design: Prospective Case Cohort

- Screening for enrollment will be undertaken in the Emergency Department (ED).
- Patients will be assigned a de-identified Research **Subject Number**
- Please note that at the discretion of the clinical study team, less than the complete ensemble of noninvasive sensing technologies may be utilized in specific cases based on patient comfort and clinical circumstances.

Placement of Sensing Technologies

[figure not shown]
- After confirmation of inclusion criteria, the absence of exclusion criteria, and informed consent is documented, trained research personnel will apply all sensors described below to appropriate locations on the patient's skin.
- Patients will already have undergone application of the ECG and pulse ox plethysmography disposables as part of normal clinical monitoring. These will be left in place and the ECG and plethysmography data will be shared with our prototype data collection system in a manner that does not interfere with the clinical monitor electrodes. The study monitor data will be acquired via iCollect software manufactured by GE. The software collects biometric data (e.g. EKG, SpO2) from clinical monitors without any imbedded PHI.

- Two SwissTom EIT arrays will be placed per subject: 1) around the thorax at the anatomic nipple line, and 2) the second alternating patient to patient between the upper abdomen at the level of the liver-spleen and the proximal thigh at the femur mid-shaft.
- **NIRS** – 3 locations, 1 probe per location: upper chest in region of thoracic EIT, and 1 either upper thigh or upper arm.
- Three sets of four ScioSpec EIS electrodes (I+, V+, V-, I-). V electrodes are placed medially to I electrodes.
 - 1st set – is applied on the torso just above the upper SwissTom arrays, I+ and V+ on the right mid-axillary line and V- and I- on the left mid-axillary line.

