SwissTom Impedance Tomography, NIRS Spectroscopy and ScioSpec Bioimpedance raw signals are all stored in a live, streaming fashion directly on an internal hard drive. All of this data is non-PHI and completely de-identified – only the subject number is incorporated into the file name. Similarly, any data collected by iCollect (mentioned above) has absolutely no PHI embedded within it and is live-captured and saved on an internal hard drive. At the end of the experiment all of this non-PHI, de-identified data will be uploaded to a secure cloud-based drive that has been approved by the participating institutions.

Data Analysis

At the completion of the study, the full data set will be used to define the performance of the Phase II algorithm with respect to the pre-specified performance criteria.

Data analysis will include the following steps:

- 1) **Data cleaning, filtering and validation:** All data will be processed to ensure that patterns are consistent with the underlying physiology. Any physiologically incorrect data will indicate issues related to loose electrodes, malfunctioning sensors,

etc. Such data will be filtered and cleaned to ensure that only meaningful data is used for algorithm testing.

- 2) **Data transformation and feature generation:** The cleaned, validated data will be transformed through a series of processing steps to generate the necessary features to be used in the supervised machine learning algorithms as predictors.
- 3) **Classification:** The features will then be used to generate machine learning-based predictions. These predictions will be compared against the ground reality of the patient's status to evaluate the algorithm performance.

Algorithm Performance Criteria: the algorithms developed will be trained to alarm under two circumstances indicating significant risk of ongoing hemorrhage progressing to shock: 1) a change from baseline, 2) development of prespecified patterns.

Performance will be judged on the basis of:

1. time of alarm before onset of deterioration
2. sensitivity, specificity, PPV, NPV for alarm/no alarm outcome
3. ROC curve and AUC for alarm/no alarm outcome
4. false-positive and false-negative rates

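### One lactate result above 4 counts as deterioration whenever it was drawn and whether it is rising or falling, and lead time can absorb laboratory delay

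*Combined protocol and SAP*

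**What the plan says.** The composite is introduced with "Definition of hemodynamic deterioration - any of", so one criterion is enough. Three of the five are anchored in time or to the patient's own starting point:

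- Heart rate: "20% increase in HR from baseline".
- Mean arterial pressure: "15% decrease in MAP from baseline".
- Systolic pressure: "A significant period (greater than 5 min.) of systolic blood pressure less than 90 associated with a heart rate greater than 110".

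The lactate criterion reads "A blood lactate result greater than 4 without nontraumatic causes of lactic acidosis". Its only qualifier concerns cause. It gives no unit, baseline, direction, repeat or sampling window.

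Among the inclusion criteria, the physiological limits are consciousness level and "Triage systolic blood pressure greater than 90 and heart rate less than 120". The exclusion criteria add oxygen saturation and a need for ongoing fluid or pressor support. None mentions lactate. Under Screening and Enrollment, the people approached have already been evaluated in the trauma room and are "currently being observed in a general ED bed who had met inclusion criteria". Sensors are applied only after consent.

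The first item under Algorithm Performance Criteria is "time of alarm before onset of deterioration". Onset is not defined there or elsewhere. Routine care is unchanged and no study lactate is required. The chart data list in Patient Case Methods includes neither a lactate value nor a sample time.

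**The concern.** A word such as deterioration implies getting worse, and the heart-rate and pressure-change criteria build that in. The lactate criterion does not. A patient whose lactate was raised on arrival can pass entry and already satisfy the event definition before recording begins. A patient whose lactate is clearing during monitoring can satisfy it too. Re-checking vital signs at sensor start would detect neither.

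Two things are at stake. The first is the deterioration label, which would include patients with no new decline. The second is lead time, the first performance criterion. A blood sample reflects the patient when it was drawn, but the plan does not say whether onset is the draw, the posting of the result, or another time.

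**Working it through.** The plan gives no lactate figure to reproduce, so the check applies its wording to constructed records. All lactate values, times and rates below are assumptions.

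**Label.** The literal rule is: event if any lactate exceeds 4.

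| Record | Change | Literal rule | What happened |
|---|---|---|---|
| 5.2 drawn and reported before sensor start, no repeat | none known | event | present before recording; no alarm could precede it |
| 5.2 before sensor start, 4.3 three hours later | 4.3 − 5.2 = −0.9 (−17%) | event | clearing, still above 4 |

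Neither record shows worsening after sensor start, and nothing in the criterion removes either one.

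**Lead time.** Let D be the draw-to-result delay. Then:

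lead dated by result = lead dated by collection + D.

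Take a sample drawn at 10:00, sensors on at 10:45, alarm at 10:50 and result posted at 11:00, so D = 60 minutes.

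- Dated by result: 11:00 − 10:50 = +10 minutes.
- Dated by collection: 10:00 − 10:50 = −50 minutes.
- Difference: 60 minutes, which is D.

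The sign changes because the draw precedes the alarm and the result follows it. In this record that requires D above 50 minutes. With D of 15 or 30 minutes the result is posted at 10:15 or 10:30, before the sensors are on, and no positive lead can be earned. Where the alarm precedes the draw it is early under either dating, but D still lengthens the figure: 10 minutes to the draw with D = 30 reads as 40.

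**Illustration of label error, if this composite is the reference standard.** Assume 480 patients, 10% true deterioration (T = 48), sensitivity and specificity both 0.90, and a fraction f of the other 432 scored only because of an old or clearing lactate (F = 432f). Assume these patients trigger alarms at the non-deteriorating rate of 0.10.

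Observed sensitivity = (48 × 0.90 + F × 0.10) / (48 + F)

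| f | F | F / (48 + F) | Observed sensitivity |
|---|---|---|---|
| 1% | 4.3 | 8% | 0.83 |
| 2% | 8.6 | 15% | 0.78 |
| 5% | 21.6 | 31% | 0.65 |
| 10% | 43.2 | 47% | 0.52 |

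This error counts against the device, whereas the delay error favours it. The documents give no basis for choosing f.

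**The case against.** The strongest reply is that the lead-time half is conditional. A reader might infer that every lactate-defined event is overstated by the laboratory turnaround, because the criterion speaks of a *result*. The documents do not support that. The word may mean only a laboratory value, and no section dates onset by posting. Onset is undefined for all five criteria, not just lactate. Heart rate or pressure may cross its limit first, in which case lactate does not set onset. A result posted before sensor start earns no positive lead. All of this stands, so the delay can be credited but is not shown to be.

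A reader might also try to size the problem. A lognormal first lactate with median 1.5 to 2.0 and log-SD 0.50 to 0.55 puts 2.5% to 10.4% of patients above 4, or 12 to 50 of 480. The arithmetic is right, but it does not measure the harm. It assumes all 480 are sampled, uses parameters not found in the documents, and ignores the exclusion of nontraumatic causes. It also counts high first values, not clearing repeats or results that straddle an alarm. Expressing a 15- to 60-minute delay as 4% to 17% of six hours (15/360 to 60/360) fails as well, because six hours is the stop rule for patients who stay stable.

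Next, two investigators adjudicate likely ongoing hemorrhage from the chart, without reference to the algorithm results, and might discount an old or falling value. That is fair, but no rule tells them to, and their categories carry no onset time. It does mean that any effect on sensitivity or AUC depends on which label the Data Analysis section intends as the patient's true status.

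Finally, warning before a result is known is a defensible quantity. It is still a different one from warning before deterioration, and the plan should say which it reports.

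**Conclusion.** The labelling defect holds on the text alone. Any lactate above 4 without a nontraumatic cause is an event, including one already present before sensor start and one that is falling. This follows from the criterion's wording, the absence of a lactate entry limit and the timing of enrolment.

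The lead-time defect holds conditionally. Delay can be credited as warning if onset is taken as the posting of the result, lactate is the first criterion met, and the draw and the result fall on either side of the alarm. The open definition of onset permits this without requiring it.

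Neither size can be estimated, because the documents give no lactate distribution, sampling frequency or turnaround. The illustrations show direction and mechanism only. Harm is established for the deterioration label and possible for lead time. For sensitivity, specificity and AUC it depends on the reference standard. The threshold of 4 is a clinical matter and is not questioned here. The point is worth settling before the performance analysis.

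**What to change.** Leave the threshold unchanged and amend the definition and the analysis as follows:

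1. Count lactate as a deterioration onset only when the sample was collected after sensor start, and date onset by collection time.
2. Treat a value above 4 collected before sensor start as baseline status. Report it, leave it out of lead time, and do not score a later value that is no higher than that baseline as a new event.
3. State how baseline-high patients are handled in performance criteria 2 to 4 (sensitivity, specificity and predictive values; ROC and AUC; false-positive and false-negative rates).
4. Report lead time with and without events defined by lactate alone.
5. Add the value and collection time of each lactate sample to the chart data list in Patient Case Methods.

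The cost is a few chart fields, fewer lactate-defined events and possibly a shorter reported lead time. One ambiguity remains: a first sample drawn just after sensor start, with no earlier value, cannot be classed as new or pre-existing. Such cases should be flagged.

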Power and Sample Size: We anticipate acquiring data from every enrolled subject. Power and sample size calculations indicate that a sample size of 480 subjects should be sufficient to: 1) further identify the minimal subset of noninvasive measurement technologies necessary for the desired diagnostic performance, 2) validate the existing algorithms, and 3) initially train a human clinical iteration of the algorithms, with a sufficient degree of accuracy ($p < 0.05$ for ROC-AUC).

Enrolled patients will undergo standard electrocardiogram (3-lead) and oxygen saturation continuous monitoring.

In addition to these standard physiologic measurements, as a part of research, we will also acquire the following non-invasive optical and impedance measurements. All of these devices have been previously validated as non-invasive and safe in humans.

The clinicians providing care to the patient will be blind with respect to the measurements from these devices.

General Approach to Minimize Risk

This protocol will be minimal risk to patients as all these technologies have been robustly demonstrated to be safe (see below). There is minimal risk associated with placement of these devices and they can be removed at any time. They don't interfere with standard equipment used in clinical management of trauma patients. As described above, clinical management of the patient will not be affected by the study intervention.

Protection: Each subject will give informed consent after all questions have been answered by a study team member. Confidentiality of data will be assured by study specific coding of subject identities. No identified individual data will be presented or published; rather, group mean data will serve as the basis for comparisons. Procedures used in this study are performed regularly in the clinical setting by the investigators.

Any original signed paper consent documents, as well as any hard copy of study documents will be stored in a locked cabinet at Baystate Medical Center. Any electronic patient information will be stored on REDCap, a secure online database that is password-protected and only accessible by study personnel.

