Uploaded de-identified data is stored in a secure server room at the Thayer School of Engineering and backed up nightly to a secure offsite facility operated by Dartmouth College. Access is limited to authorized users, based on the security model of the share. Access to data is via SMB or kerberized NFS protocols and allowed only from on-campus locations or over VPN. For any data shares that store Level 3 data (according to Dartmouth DISC policy), access is only allowed via VPN or from properly secured on-campus systems to ensure two-factor security.

Potential Risks:

The adhesives used on the electrodes can cause skin irritation. This risk should not be greater than that caused by our hospital ECG monitor. Tomography (EIT) and Near Infrared Spectroscopy (NIRS) may carry a risk of electrical sensation/shock or light exposure to eyes if the equipment malfunctions or gets displaced. There may be additional risks in this study which are not yet known.

Benefits:

None beyond participation in biomedical research.

Inclusion of Women and Minorities:

These groups will not be excluded from screening or enrollment in this convenience sample.

Inclusion of Children:

Children less than 18 years of age are excluded.

Inclusion of Adults with Impaired Decision-making Capacity: Adults with impaired decision-making capacity will not be included in this study.

Safety monitoring:

As this is a minimal risk, non-invasive study, we do not anticipate major changes in risks and benefits. Continual and prompt monitoring by the Principal Investigator of any unanticipated problems will be reported to the IRB and the sponsor.

No Significant Risk

All modules within the prototype are designed to conform to the International Electrotechnical Commission (IEC) 60601-1 safety standard for medical devices. Specifically, all devices are below the safety limits defined for Patient Auxiliary Currents which specifies that the maximum injected current for a diagnostic device is:

1. < 100 uA for frequencies < 1 kHz
2. < 100uA between 1 kHz and 100 kHz
3. < 10 mA for frequencies > 100 kHz

All devices are operated so the patient is floating with respect to the circuitry of the devices; ensuring that the patient is not exposed to appreciable DC current levels.

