Appendix I

Description of Impedance and Infrared Subsystems of the Mark I

SwissTom Electrical Impedance Tomography (EIT) System:

Name of device: Pioneer Set (Electrical Impedance Tomography System)

Device Manufacturer: SwissTom AG (Parent company SenTec AG)

This device monitors dynamically changing perfusion physiology. To record multiplexed impedance signature from two arrays of 16 electrodes, one array is placed around the thorax above the nipple line and the second array alternates patient to patient between the upper abdomen at the level of the liver-spleen, and the proximal thigh at the femur mid-shaft. The Impedances are recorded between multiple sets of electrodes.

SwissTom developed a clinical EIT system that is approved for pulmonary imaging. This Pioneer system is their research platform that has similar functionality and safety performance to their clinical system but provides research teams with access to raw data and additional functionality for specifying imaging parameters (e.g. control of frame rates, signal frequency acquisition, electrode drive patterns).

Continuous-wave Near-Infrared Spectroscopy (CW-NIRS) Device, custom built:

The device is built on an Ocean Optics FLAME USB Spectrometers, with two OSRAM 4736 NIR LEDs in plastic holders meant to be taped or strapped to the patient on the chest/torso. Probe holders are designed to collect light from surface of skin by means of a mirror and collimator. The device will collect data on light attenuation of muscle in models of shock/trauma. The light output is below the ANSI limits for maximum permissible skin exposure.

ScioSpec MultiChannel Electrical Impedance Spectroscopy (EIS) System:

Name of device: ISX-Mini (MultiChannel Electrical Impedance Spectroscopy System)
Device Manufacturer: ScioSpec

To record multiplexed impedance signatures- arrays of 4 electrodes is placed around the thorax, arm, and thigh of the patient and impedance spectroscopy signatures are recorded. This device monitors dynamically changing intrathoracic and intra-abdominal physiology.

3

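### The second EIT site follows predictable, unconcealed alternation, so any choice between abdomen and thigh is open to selection bias

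*Combined protocol and SAP*

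**What the plan says.** Placement of Sensing Technologies gives each patient two EIT arrays: one on the thorax, and "the second alternating patient to patient between the upper abdomen at the level of the liver-spleen and the proximal thigh". Appendix I repeats the rule ("the second array alternates patient to patient between the upper abdomen at the level of the liver-spleen"), and so does the wearables list under First Generation Prototype. No random sequence and no concealment are described.

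Exclusion criterion 7 reads: "Anatomical abnormality or injury that would prevent placement of the electro-optical electrodes". It names no site. On sequence, the plan states: "After confirmation of inclusion criteria, the absence of exclusion criteria, and informed consent is documented, trained research personnel will apply all sensors". It does not say when the second site is fixed or made known to staff.

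Under Study Design, "less than the complete ensemble of noninvasive sensing technologies may be utilized in specific cases based on patient comfort and clinical circumstances". No rule says how an omitted second array is handled. Inclusion of Women and Minorities shows how patients are recruited: "These groups will not be excluded from screening or enrollment in this convenience sample".

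Power and Sample Size gives as its first purpose for 480 patients to "further identify the minimal subset of noninvasive measurement technologies necessary for the desired diagnostic performance". The Background, under Progress to Date, reports that both technologies and anatomical locations were ranked in earlier work, and that this ranking will guide pruning.

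The chart items listed in Patient Case Methods are gender, age by decade, height, weight, medications and vital signs. Injury location, mechanism and severity are not listed.

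**The concern.** No patient has both second sites, so abdomen against thigh can only be compared between patients. Under strict alternation, anyone who knows the last placement knows the next one. In a convenience sample, that knowledge can influence whom staff approach, how they judge exclusion 7, and whether they leave the array off. An abdominal wound is a reason to pass over a patient, or drop the array, on an abdomen turn. It is not a reason on a thigh turn, and the reverse holds for a thigh wound.

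The decision at stake is which sites to keep. The abdominal array lies at liver-spleen level. If patients with abdominal injury are less often enrolled or measured on abdomen turns, that array is judged with fewer of the patients in whom it might add most. A difference in AUC could then reflect who was enrolled rather than where the electrodes were. With injury location not among the extracted items, the imbalance could be neither seen nor adjusted for from the planned data.

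**Working it through.** The plan gives no figure for this comparison, so there is none to reproduce. Its total of 480 cannot be rebuilt either, because power, target AUC and event rate are not stated. What can be checked is how large an imbalance could be and how precise a site comparison would be.

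**Group size.** 480 / 2 = 240 per second site, if every patient receives both arrays.

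**Injury mix.** All rates here are assumed. Candidates: 25% torso injury, 25% leg injury, 50% other, with event rates of 20%, 10% and 5%. Suppose exclusion 7 is judged only against the next site and removes a fraction x of torso-injured patients on abdomen turns and the same fraction of leg-injured patients on thigh turns. Both groups then keep 1 − 0.25x of candidates.

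- Torso share, abdomen group: 0.25(1 − x) / (1 − 0.25x)
- Torso share, thigh group: 0.25 / (1 − 0.25x)
- Event rate, abdomen group: [0.05(1 − x) + 0.025 + 0.025] / (1 − 0.25x)
- Event rate, thigh group: [0.05 + 0.025(1 − x) + 0.025] / (1 − 0.25x)

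| x | Torso share, abdomen vs thigh | Event rate, abdomen vs thigh |
|---|---|---|
| 0% | 25.0% vs 25.0% | 10.0% vs 10.0% |
| 10% | 23.1% vs 25.6% | 9.7% vs 10.0% |
| 30% | 18.9% vs 27.0% | 9.2% vs 10.0% |
| 50% | 14.3% vs 28.6% | 8.6% vs 10.0% |

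The event rates stay close while the mix of cases moves. At x = 30%, torso injury supplies 0.035 / 0.085 = 41% of events in the abdomen group and 0.05 / 0.0925 = 54% in the thigh group.

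**Upper bound (assumed).** Let 10% of candidates have an abdominal injury that bars the array (25% bleed) and 10% a thigh injury that bars it (10% bleed), with the rest bleeding at 8%. Every barred patient is excluded on the matching turn.

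- Abdomen group: (0.10 × 0.10 + 0.80 × 0.08) / 0.90 = 0.074 / 0.90 = 8.2% bleed
- Thigh group: (0.10 × 0.25 + 0.80 × 0.08) / 0.90 = 0.089 / 0.90 = 9.9% bleed
- Share of bleeders with an array-barring abdominal injury: 0% against 0.025 / 0.089 = 28%

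With 5% rather than 10% barred at the abdomen, the 28% becomes 0.0125 / (0.0125 + 0.85 × 0.08) = 16%. With a 15% bleed rate in that stratum, it becomes 0.015 / (0.015 + 0.064) = 19%.

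**Lower bound.** If exclusion 7 is judged against both candidate sites for everyone, the same patients are removed on every turn and the criterion creates no expected difference. Selective approach and selective omission remain possible, and the documents give nothing from which to size them.

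**Precision of a site comparison.** Hanley-McNeil, with AUC = A, n1 events and n0 non-events:

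SE² = [A(1 − A) + (n1 − 1)(A/(2 − A) − A²) + (n0 − 1)(2A²/(1 + A) − A²)] / (n1 n0)

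For A = 0.80 and an assumed 10% event rate, n1 = 24 and n0 = 216. SE² = (0.160 + 0.613 + 15.289) / 5184 = 0.0031, so SE = 0.056. For two independent groups, the 95% half-width is 1.96 × √2 × 0.056 = 0.15. At event rates of 5%, 10% and 20%, the half-width is about 0.22, 0.15 and 0.11 for A = 0.80, and 0.17, 0.12 and 0.09 for A = 0.90.

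**The case against.** The strongest reply is that the plan promises no such comparison. The sample-size paragraph speaks of technologies, not locations. The stated aims are to evaluate the prototype, validate the Phase II algorithm and re-train it, and the performance criteria concern the alarm. This stands. Choosing between sites is an inference from the Background's account of ranking locations and pruning. It is a fair inference, but no contrast is prespecified.

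A reader might go further and infer that the two groups will differ and cannot be compared fairly. The documents do not support that:

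- Exclusion 7 refers to the electrodes as a whole, and judged against all sites it produces no imbalance.
- Placement of Sensing Technologies keeps the second EIS set on the trunk in thigh-array patients, so a truncal injury could block those patients too. Appendix I and the EIS table in Appendix II instead list a thigh or leg position, which needs reconciling.
- Staff may omit an array instead of excluding the patient. That makes the problem partly one of selective missing data rather than entry.
- The 0% against 28% contrast is an upper bound on assumed inputs. It concerns only injuries that physically bar electrodes, not all abdominal injury.
- A gap in prevalence does not by itself change AUC, and no AUC bias has been shown.

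The comparison would also be imprecise even with perfect randomisation, as the half-widths show.

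Two replies do not remove the point. The thorax array on everyone allows a within-patient estimate of what each second site adds, but that increment still depends on which patients are in the group. Similar event rates are not reassuring either, because AUC can depend on the spectrum of cases.

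**Conclusion.** The concern holds in a limited form. Predictable, unconcealed alternation in a convenience sample, with an exclusion that names no site and a discretion to omit sensors, means that the abdomen and thigh groups may differ in injury mix. The listed chart items could not reveal it. Any choice between the two second sites would be a between-patient comparison open to selection bias.

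The size is unknown. Exclusion 7 contributes nothing under an all-sites reading. Under a next-site reading with the assumed rates above, the gap in torso injury runs from 2.5 percentage points (25.6 − 23.1) at 10% removal to 14.3 points (28.6 − 14.3) at 50%. The main validation of the Phase II algorithm is not undermined. This is a cheap improvement that protects a later pruning decision, not a defect in the central aim.

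**What to change.** - Replace alternation with a computer-generated blocked list held in REDCap, which the study already uses. Reveal the site only after consent and confirmed eligibility.
- State which sites exclusion 7 covers, and apply it in the same way whichever site will be assigned.
- If the assigned array then cannot be placed, record it as omitted under the existing Study Design discretion. Keep the patient in the assigned-site group for any site comparison.
- Extract injury location from the chart, and report omitted arrays by assigned site.
- State that about 240 patients inform each second site.

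The total of 480 does not change. The cost is a little set-up work, some protocol wording, and some patients with a missing second array. On the upper-bound inputs, and if no one is excluded on this ground, that is 10% of each group, or 24 of 240.

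The stricter alternative, requiring every patient to be eligible at all sites, is a real trade-off. On the same inputs it raises exclusions from 10% to 20% of candidates. Expected bleeders among 480 fall from 240 × 0.082 + 240 × 0.099, about 43, to 480 × 0.064 / 0.80, about 38. It also removes every patient with an array-barring abdominal injury from the main validation. The omission rule above avoids that loss.
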